# **13.6 Exploratory Analyses**

Variables involved in exploratory analyses will be examined graphically and summarized by descriptive statistics. Data transformation may be applied to quantitative variables prior to analyses if deemed necessary.

Bivariate association analyses will be conducted to evaluate the associations between exploratory biomarkers and clinical outcomes and adverse events for the objectives listed in 1.4. The analyses will be performed for each group separately and/or combined as deemed appropriate. Specifically, Pearson or Kendall's tau correlation coefficients will be calculated to evaluate the association between quantitative variables, Chi-squared tests or Fisher's exact tests will be used to examine the association between categorical or ordinal variables, and ANOVA will be performed to study the association between a quantitative variable and a categorical variable. The association between biomarkers and clinical outcomes (PFS and OS) will be evaluated using Cox regression and elastic net regularized regression for variable selection. For markers with multiple measurements over time, data at a specific time point or change from pre-treatment will be used in the above bivariate analyses as deemed appropriate.

Changes in markers pre- and post- treatment will be assessed using paired t-tests.

Between-group comparisons will be conducted for PFS, OS, TIL density, interferon and cell cycle-related genetic signatures, and IHC expression. Survival analyses via Kaplan-Meier curves and log-rank tests will be used to estimate and compare PFS, second PFS, and OS between Group A, Group B, and Group C.

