# **1.4 Exploratory Objectives**

To evaluate the associations between exploratory biomarkers, clinical outcomes and adverse events which include:

• Exploring the influence of VB-111 on cell cycle-related genetic signatures or IFN-γ associated signatures within the tumor microenvironment and correlating with clinical responses.

- Exploring the influence of VB-111 on oligoclonal T-cell populations within tumor tissue and peripheral blood and correlating with clinical responses.
- Exploring the influence of VB-111 on specific MRI parameters, and correlating with tumor and peripheral blood immune responses.
- Estimating the efficacy of VB-111 by PFS and OS as defined by RANO.
- Estimating the efficacy of VB-111 by PFS6, PFS and OS as defined by iRANO.

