# 5.4 Trial Blinding/Masking

Pre-operative treatment will be blinded; therefore, the treating investigator and subject will not know whether VB-111 or placebo is administered. An unblinded pharmacist or designee not involved in other study assessments will prepare the Pre-operative study drug of VB-111/Placebo. Post-operatively, treatment will be unblinded.

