# 8.1.9 Placebo

Normal Saline (NS) will be used as placebo in this study. NS will be provided by the study site.

A randomized, placebo controlled phase II, surgical trial to evaluate early immunologic pharmacodynamic parameters for the viral cancer therapy ofranergene obadenovec (VB-111) in patients with surgically accessible recurrent/progressive glioblastoma Version 3.0 February 18, 2021

Placebo should be kept at room temperature until administration. The following steps should be followed:

- Determine the volume to be applied according to the participant's weight (see Table 3).
- For patients who weigh >50kg: Place 50ml of saline (brought to room temperature) in a 60ml sterile syringe or select a 50ml saline bag.
- For patients who weigh <50kg: Place 35 ml of saline (brought to room temperature) in a 60ml sterile syringe
- After completing the preparation, record medication assigned to the participant in the participant dispensing log.

Placebo will be administered to participants assigned to Group B and Group C 21±7 days prior to surgery.

Both placebo and VB-111 infusion solutions are clear solutions that are visually indistinguishable. A dispensing log will be kept by the investigational pharmacist or designee, in which he/she will record the date(s) and details of the Placebo dispensed for each participant. The dispensing log will be made available to the study monitor who will verify accountability during the course of the study.

The preparation of the Neoadjuvant dose of VB-111/placebo will be performed by an unblinded site pharmacist or designee who is not involved in other study activities.

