## 9.3 Immunophenotyping

Tumor and peripheral blood T cell subsets and activation markers will be assessed with mass cytometry high dimensional analysis to identify immune cell subsets that expand or contract in an unbiased fashion during treatment with VB-111. The CD4/CD8 ratio, Treg populations (CD3+,CD4+CD25+CD127low), activation (CD3+CD8+CD25/69), MDSC (CD33+HLA-DrlowCD11b+PD-L1+), negative costimulatory markers (CD3+CD4/8+PD-1+, CD3+CD4/8+CTLA-4+) will be determined at each time point. CyToF analysis will be performed on PBMC obtained from FicoII density gradient separation of whole blood. Blood draws for this testing will be performed pre-treatment, pre-surgery, and with every MRI scan obtained for tumor status. Guidance on peripheral blood collection, processing and shipping is provided in Table 4 below.

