#### **Imaging Correlates Table**

Correlative Objective	Imaging Technique	Organ(s) Scanned (Timing of Scans)	Mandatory
(Lead PI, Site)			/Optional
Accurate distinction between tumor and	MRI (ADC, Perfusion)	Brain (pre- Neo-adjuvant treatment, Pre-surgery, post-	Mandatory
inflammation ([name], UCLA)		surgery, every 6 weeks during adjuvant treatment, EOT)	

A randomized, placebo controlled phase II, surgical trial to evaluate early immunologic pharmacodynamic parameters for the viral cancer therapy ofranergene obadenovec (VB-111) in patients with surgically accessible recurrent/progressive glioblastoma Version 3.0 February 18, 2021

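### Section 13.6 names only within-person paired t-tests for change in the MRI parameters and mass-cytometry blood markers, leaving the blinded pre-operative placebo groups unused as a control

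*Combined protocol and SAP*

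**What the plan says.** Section 13.6 deals with marker change in one sentence: "Changes in markers pre- and post- treatment will be assessed using paired t-tests". It names no markers, groups, time points, alpha or sidedness. The next sentence reads: "Between-group comparisons will be conducted for PFS, OS, TIL density, interferon and cell cycle-related genetic signatures, and IHC expression". MRI parameters and mass-cytometry subsets are not in that list.

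Section 1.4 sets as an objective: "Exploring the influence of VB-111 on specific MRI parameters, and correlating with tumor and peripheral blood immune responses".

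The measurements are taken before dosing and again before surgery. For mass cytometry, section 9.3 says: "Blood draws for this testing will be performed pre-treatment, pre-surgery, and with every MRI scan obtained for tumor status". For MRI, the Imaging Correlates Table (ADC, perfusion; mandatory) gives a timing entry that begins "Brain (pre- Neo-adjuvant treatment, Pre-surgery, post" and goes on through adjuvant treatment. Neither place limits the schedule to a group. The Exploratory Biomarkers Table marks mass cytometry as optional.

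On the control, section 8.1.9 says: "Placebo will be administered to participants assigned to Group B and Group C 21±7 days prior to surgery". Section 5.4 says: "Pre-operative treatment will be blinded; therefore, the treating investigator and subject will not know whether VB-111 or placebo is administered". After surgery, treatment is open.

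**The concern.** A paired t-test within treated participants asks whether the marker moved. The section 1.4 objective for MRI asks whether VB-111 moved it. The two questions coincide only if nothing else changes between the measurements.

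The documents give reasons to expect other change. Participants enter with progressing tumor (section 3.1). Their steroid dose may be falling at entry (section 3.1.8). Dexamethasone may be given around either the VB-111 or the placebo infusion (section 5.7.2). For MRI, the calendar's only pre-dose scan is the screening scan. It may precede enrollment by up to 14 days, dosing follows within 5 days of randomization, and surgery is 14 to 28 days after dosing. If registration and randomization fall on the same day, the two scans can be 14 + 5 + 28 = 47 days apart.

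The trial's declared purpose is early pharmacodynamic evaluation. A false marker signal could be carried into later work on the drug.

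**Working it through.** **Which tests apply to which markers**

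| Marker | Between-group comparison named? |
|---|---|
| TIL density | Yes, A vs B+C (13.3, 13.4); also in 13.6 |
| Expanded TCR clones in blood | Yes, A+B vs C (13.4) |
| Interferon and cell-cycle signatures, IHC | Yes (13.6) |
| MRI parameters (ADC, perfusion) | No |
| Mass-cytometry blood markers | No |

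The gap is confined to the last two rows.

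**The plan's own figure.** None is given for the paired tests. The only stated power, 84% for TIL density (15 vs 30, difference 0.8 SD, one-sided 5%), concerns a different test. The noncentral-t formula gives 80.1% for that design. The mismatch is a separate matter and does not bear on this point.

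**Inputs.** Group A n = 15 and B+C n = 30 (13.3). Two-sided alpha of 5% is an assumption, because 13.6 gives none. The drift, as a multiple of the SD of the change score, is also an assumption. The true drug effect is set to zero.

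**Paired test in Group A.** With mean change δ SD, the statistic follows a noncentral t with n − 1 = 14 degrees of freedom and noncentrality δ√15 = 3.873δ. The test rejects when it exceeds the two-sided 5% critical value in either direction.

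**Controlled comparison.** The difference in mean change is (drift + effect) − drift = effect, so drift common to the groups cancels. The rejection rate of a two-sample t-test of change, 15 vs 30, was checked by simulation (40,000 runs per row, equal SDs).

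| Assumed drift (SD of change) | Noncentrality | Paired t, Group A, n = 15 | Change, A vs B+C |
|---|---|---|---|
| 0 | 0 | 5.0% | 4.9% |
| 0.2 | 0.775 | 11.2% | 4.9% |
| 0.3 | 1.162 | 19.2% | 5.0% |
| 0.5 | 1.936 | 43.8% | 5.0% |
| 0.8 | 3.098 | 82.1% | 5.0% |

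**Cost in power.** For a true effect of 0.8 SD and no drift, the paired test in 15 has 82% two-sided power. The two-sample comparison has noncentrality 0.8 × √(15 × 30/45) = 2.530 and 70% two-sided power (80% one-sided).

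**The case against.** The strongest reply is that these analyses are exploratory and that 13.6 nowhere says a significant paired test establishes a VB-111 effect. The sentence does not confine the tests to Group A, so they could be run in each group, and drift would then show in B and C. Section 13 also requires changes to exploratory analyses to be listed in the study report. All of this stands, and it sets the severity.

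It does not remove the gap, because comparing significance across groups is not a test of their difference. With no drug effect, the chance that A is significant while pooled B+C (n = 30; paired rejection 35.5%, 75.4%, 98.8%) is not would be:

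- drift 0.3: 0.192 × (1 − 0.355) = 12%
- drift 0.5: 0.438 × (1 − 0.754) = 11%
- drift 0.8: 0.821 × (1 − 0.988) = 1%

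The error rate of that informal comparison depends on the unknown drift.

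A second reply is that 13.6 provides ANOVA and change scores: "data at a specific time point or change from pre-treatment will be used in the above bivariate analyses as deemed appropriate". That paragraph concerns associations of biomarkers with clinical outcomes and adverse events. Treatment group is not named as the factor.

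A third reply is that the stated aim of mass cytometry in 9.3 is to find subsets that expand or contract during VB-111 treatment, which is close to within-person description. This is fair: the mismatch between objective and test is clear for MRI and weaker for cytometry.

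A reader might also infer more than the documents support:

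- That all blood immune markers lack a control. Expanded TCR clones have a two-sample test in 13.4.
- That drift will be reported as a drug effect. The text supports only that it can be.
- That the blinded control extends past surgery. After surgery treatment is open, Group B receives VB-111 and Group C receives standard of care.
- That 30 VB-111 participants could enter the pre-operative test. Only Group A, 15 participants, receives VB-111 before surgery.

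**Conclusion.** The point holds for two exploratory marker families over the pre-operative interval: MRI parameters and mass-cytometry blood markers. For these, the plan names an uncontrolled test of change although a randomized, blinded placebo comparison is available from data already scheduled.

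The tabulated false-positive rates are illustrative. They rest on assumed drift, a two-sided 5% level, equal SDs of change and 15 complete pairs. Because mass cytometry is optional, 15 and 30 are upper limits for it. That the schedules cover all three groups is an inference from the absence of any restriction, but a reasonable one.

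Severity is low. The primary TIL comparison, the secondary endpoints, the gene signatures and IHC are unaffected.

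**What to change.** Amend 13.6 to say that the pre-surgery value of each MRI parameter and mass-cytometry marker is compared between Group A and Group B+C by ANCOVA, with the pre-treatment value and the tumor-size stratum as covariates. Report it as exploratory, with the number of markers examined. State the analysis set and how many participants have both measurements. Keep the paired t-tests as within-group descriptions.

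Do not use the same ANCOVA after surgery, A+B vs C, as a test of drug effect. That contrast is open-label against active therapy, and for MRI the pre-treatment covariate describes a tumor that has since been resected. If a post-operative comparison is wanted, label it an open-label comparison with standard of care and use the post-operative scan as the MRI baseline, as section 11 already does for progression.

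The cost is SAP wording, with no new samples, scans or visits. The downside is the lower power shown above (70% against 82% two-sided at 0.8 SD). ANCOVA recovers part of it: with equal variances at the two times, its variance relative to a change-score comparison is (1 − ρ²)/(2(1 − ρ)) = (1 + ρ)/2, or 0.75 at an assumed correlation ρ of 0.5.

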# 5.5 Stratification

Randomization will be stratified according to baseline tumor size ( $\leq 15$  cc, >15 cc).

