## 13.3 Sample Size Consideration

This is a randomized, controlled, blinded, phase II, surgical trial to evaluate early immunologic pharmacodynamic parameters for the viral cancer therapy VB-111 in participants with surgically accessible recurrent/progressive glioblastoma (rGBM). Participants will be randomly assigned to group A or B or C with a 1:1: 1 randomization ratio prior to surgery. The primary hypothesis is that VB-111 can generate effective anti-tumor immune responses in the form of a statistically significant increase in TIL density comparing Group A (neoadjuvant/adjuvant) vs combined control group (Group B+C).

Based on our preliminary data, the mean of TIL density is estimated to be 0.4 (T cells per nucleated cell) (SD=0.5) in the combined control group (Group B and C). Comparing Group A vs Group B+C at an alpha level of 0.05 (1-sided) using a stratified two-sample t-test, a sample size of 30 in the combined Group (B+C), and 15 in Group A (Total of 45 evaluable) allows for the detection of a standard difference in TIL density of 0.8 or larger with 84% power. Effect size is defined as Cohen's D, the difference of two population means, divided by the pooled standard deviation. [63]

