## 13.4 Efficacy Analysis

A two-sample t-test with tumor size stratification will be used to test the difference of tumor infiltrating T cell density between the two groups (Group A vs combined Group B+C). Data distribution will be examined prior to analysis. Data transformations will be performed as deemed appropriate.

For the secondary endpoint of PFS6, historical comparison data are available from a pooled analysis of Phase II experience in recurrent Grade IV gliomas who have undergone surgery either just prior to starting treatment or as part of the protocol, which documented a PFS6 rate of 10%. Group comparisons (Group A vs C; Group B vs C; Group A+B vs C) will be conducted using the exact binomial test with Bonferroni adjustment to compare PFS6 rate at one sided alpha of 5%.

For OS, analyses will be conducted using historical comparison data which are available from a pooled analysis of Phase II experience in recurrent Grade IV gliomas who have undergone surgery either just prior to starting treatment or as part of. Kaplan-Meier (KM) curves and median estimates from the KM curves will be provided as appropriate. Participants without efficacy evaluation data or without survival data will be censored at Day 1. For evaluation of the expansion of TCR clones, a two-sample T-test with Bonferroni adjustment will be used to compare the increase number of expanded TCR clones after VB-111 in Group A+B vs Group C.

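### The exploratory log-rank tests and the TCR t-test do not use the tumor-size stratum of the randomization; this matters only if tumor size is strongly prognostic

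*Combined protocol and SAP*

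**What the plan says.** Section 5.5: "Randomization will be stratified according to baseline tumor size", with two levels (up to 15 cc, above 15 cc). It is the only stratification factor.

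The primary analysis follows the randomization. Section 13.4: "A two-sample t-test with tumor size stratification will be used to test the difference of tumor infiltrating T cell density between the two groups". The power statement in 13.3 is likewise made "at an alpha level of 0.05 (1-sided) using a stratified two-sample t-test".

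The other comparisons name no stratum or covariate:
- **PFS, second PFS and OS between groups (13.6, exploratory):** "Survival analyses via Kaplan-Meier curves and log-rank tests will be used to estimate and compare PFS, second PFS, and OS", between Groups A, B and C.
- **Expanded TCR clones (13.4, secondary):** two-sample t-test with Bonferroni adjustment, A+B vs C.
- **PFS6 (13.4, secondary):** exact binomial test with Bonferroni adjustment for A vs C, B vs C and A+B vs C.
- **OS (13.4, secondary):** comparison with historical data and Kaplan-Meier estimates, so there is no randomized contrast.

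The plan gives no reason for using the stratum in one test and not in the others. Hypothesis 2 in Section 1.3 concerns survival against Group C and/or historical controls. The log-rank test in 13.6 is therefore the only planned test of OS against Group C.

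**The concern.** When randomization balances a prognostic factor, the difference between arms varies less than an unstratified test assumes. The test is then conservative and gives up power, and an unstratified hazard ratio is pulled toward 1. With 15 per group there is little power to spare.

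The omission also leaves a choice open. An analyst could use the stratum, or not, after seeing the data.

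**Working it through.** **1. The plan's own power figure.** The only one is for TIL density: the plan "allows for the detection of a standard difference in TIL density of 0.8 or larger with 84% power". The noncentrality for 30 vs 15 is 0.8 × √(30 × 15 / 45) = 0.8 × 3.162 = 2.530. The normal approximation gives Φ(2.530 − 1.645) = Φ(0.885) = 81.2%. The noncentral t gives 80.1%, with 43 df or with 42 df after a stratum term. So 84% does not reproduce at 30 vs 15. It matches a 22/23 split (84.0%), or tumor size explaining roughly 11% of TIL variance (83.6% at R² = 0.10, 84.3% at 0.12), which the plan does not state. That is a separate matter. No power is stated for any test discussed here.

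**2. Log-rank.** The statistic is Z = Σ(O − E) / √ΣV over event times. The stratified form computes O − E and V within each tumor-size stratum before summing.

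Inputs from the documents: 15 per group, hence 15 vs 15 pairwise and 30 vs 15 for A+B vs C. Assumed: exponential survival, 24 months of follow-up, one-sided 5%, the stratum hazard ratios and the share of large tumors. Setting 1 uses treatment HR 0.5, control median 8 months and 6,000 trials per cell. Setting 2 uses HR 0.51, control median 7.4 months and 8,000 trials per cell. The HR of 0.51 is the phase 2 OS figure in 2.2.2. The medians lie near that section's 223 days and 7.9 months. The Monte Carlo standard error of one power at 6,000 trials is about √(0.5 × 0.5 / 6000) = 0.65 points.

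Power in %, unstratified → stratified:

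| Groups | Stratum HR | Setting 1, 33% large | Setting 1, 50% large | Setting 2, 50% large |
|---|---|---|---|---|
| 15 vs 15 | 1 | 51.1 → 49.3 | 49.7 → 48.3 | 49.7 → 47.8 |
| 15 vs 15 | 1.5 | 50.7 → 50.5 | 50.8 → 50.9 | not run |
| 15 vs 15 | 2 | 49.5 → 51.2 | 48.4 → 51.8 | 44.9 → 47.8 |
| 15 vs 15 | 3 | 43.7 → 51.4 | 40.7 → 51.2 | 38.3 → 47.9 |
| 30 vs 15 | 1 | 63.0 → 62.4 | 62.0 → 61.0 | 61.7 → 60.5 |
| 30 vs 15 | 1.5 | 63.3 → 63.3 | 65.2 → 64.4 | not run |
| 30 vs 15 | 2 | 59.9 → 63.1 | 64.0 → 64.5 | 58.7 → 59.8 |
| 30 vs 15 | 3 | 55.3 → 63.1 | 57.5 → 65.0 | 53.0 → 59.4 |

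Two further runs at HR 0.51, 30 vs 15 and stratum HR 3 gave 53.1 → 59.2 and 52.3 → 58.2, that is 6.1 and 5.9 points.

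Type I error at 15 vs 15 and stratum HR 3 is 3.7 to 4.0% unstratified and 5.2 to 5.6% stratified. At 30 vs 15 and stratum HR 3 it is 5.1% unstratified and 6.1 to 6.7% stratified. The median Cox HR there (setting 2, true value 0.51) is 0.53 unstratified and 0.49 stratified.

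**3. TCR t-test, 30 vs 15.** Assumed: d = 0.8, one-sided 5% before Bonferroni, and tumor size explaining a share R² of the variance. With a stratum term the noncentrality becomes 2.530 / √(1 − R²). For R² = 0.20 that is 2.530 / 0.894 = 2.83. Power without → with the term: R² 0, 80.0 → 80.0; 0.05, 81.9 → 81.8; 0.10, 83.0 → 83.5; 0.20, 85.0 → 87.2.

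**4. PFS6.** At the 10% historical rate in 13.4, Group C expects 15 × 0.10 = 1.5 successes over two strata. Exact enumeration compared Fisher's test with an exact stratified conditional test (assumed treatment odds ratio 6, control rate about 10% or 15%, stratum odds ratio 1 to 4). At alpha 0.05, 15 vs 15 and a rate of about 10%, the stratified test is about 1 point worse (46.3 → 45.6, 39.2 → 38.0, 31.9 → 31.1). At 0.05/3 it is 1 to 3 points better (22.6 → 23.8, 14.6 → 16.7, 8.8 → 11.8). Over all cells it runs from 3 points worse (51.3 → 48.3) to about 5 better (21.1 → 26.5). Part of the gain appears at stratum odds ratio 1, where size predicts nothing, so it comes from the discreteness of the test.

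**The case against.** The strongest reply is that nothing in the documents shows tumor size to be strongly prognostic here. Eligibility caps the longest diameter at 4 cm (3.1.4). A 4 cm sphere holds π/6 × 4³ = 33.5 cc, and 15 cc corresponds to about 3.1 cm, so the strata divide a truncated range. Every participant is planned for resection, PFS6 runs from surgery, and the baseline scan for progression is post-operative (Section 11). Pre-surgical volume may say little about what follows. This stands, and it is why the loss can only be stated conditionally.

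The simulated test is also not exactly the planned one. Section 13.6 names neither a pooled A+B vs C log-rank test nor a one-sided level. The HR of 0.51 compares two VB-111 schedules, and the phase 3 OS HR was 1.2. This stands too. The figures show what stratifying can change, not the trial's actual power. At 30 vs 15 the stratified test's type I error is slightly above nominal, which accounts for part of its apparent gain there.

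That the log-rank tests are exploratory limits the stakes but does not remove them, since no other randomized OS comparison is planned.

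A reader might infer more than the documents support:
- **That the design loses power it had counted on.** The only power claim is for TIL density, and that test is stratified.
- **That all secondary clinical analyses are affected.** Secondary OS is a historical comparison, where a randomization stratum does not enter, and a stratified exact PFS6 test is not reliably better.
- **That a planned hazard ratio is diluted.** No between-group hazard ratio is planned; Cox regression in 13.6 serves biomarker associations.

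**Conclusion.** The inconsistency is real and minor. The stratum of the randomization is used for TIL density but not for the between-group log-rank tests or the TCR test, and no reason is given.

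For the log-rank test, the loss from ignoring the stratum is about 9 points at 15 vs 15 (range 8 to 10) and about 6 at 30 vs 15 (up to 8) if the stratum HR is 3. It is about 1 to 3 points at HR 2 and nil at 1.5. At HR 1 stratifying costs about 1 to 2 points. Conservatism was seen at 15 vs 15 with a strong stratum effect. An unstratified test is less efficient in that case, not invalid. For TCR, a tumor-size term costs essentially nothing and gains about 2 points at R² = 0.20.

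All of this rests on assumed stratum effects, shares and treatment effects. The case for stratifying is the asymmetry: a small cost if size does not matter, a larger gain if it matters strongly, and no choice left open at analysis.

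**What to change.** - **13.6:** specify that the log-rank tests for PFS, second PFS and OS are stratified by the randomization stratum (up to 15 cc, above 15 cc). If a hazard ratio is reported, take it from a Cox model stratified the same way.
- **13.4, TCR:** replace the plain two-sample t-test with a linear model holding group and tumor-size stratum, and keep the Bonferroni adjustment.
- **Sensitivity:** report the unstratified versions of both. State in advance what happens if a stratum has too few participants to contribute.
- **13.4, PFS6:** keep the exact test as planned. Any stratified exact version is a sensitivity analysis only, because the strata are sparse.
- **13.4, OS:** leave the historical comparison unchanged.

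If the sponsor prefers unstratified tests, one sentence giving the reason would also close the gap.

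The cost is a few sentences and a few lines of code, plus about 1 to 2 points of log-rank power if tumor size is not prognostic. Under Section 13, a change to an exploratory analysis can be listed in the study report. The TCR change concerns a secondary objective and is best made by amendment before the data are seen.
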